#### Why combine inositol and omega-3 fatty acids

As pediatric bipolar disorder is most commonly characterized as mixed with cooccurrence of manic and depressed symptoms, a treatment option combining agents with anti-manic and anti-depressant actions could be successful. Both omega-3 fatty acids, including EPA and DHA, and inositol have shown modest positive effects for depression, bipolar depression and, in the case of omega-3 fatty acids, mania. The mechanism of action of these agents are complementary, with omega-3 fatty acids increasing membrane fluidity and inositol working as a critical second messenger in cell processes occurring in the cell membrane. Thus from both clinical and purported mechanism standpoints, using these agents in combination makes clinical and pathophysiologic sense. Thus, we propose to study the efficacy and safety of the natural treatments of omega-3 fatty acids and inositol used singly and in combination in youth with bipolar spectrum disorders.

#### Rationale

Emerging research suggests that inositol may have modest effects in the treatment of depression, but there have been no studies in children. Similar to the omega-3 fatty acids, inositol is well tolerated. Given that these nutritional supplements show promise in the treatment of mood disorders but to small effect, we propose to study the possible additive effect of combining these two alternative treatments in youth with bipolar spectrum disorders, an area of significant need.

We propose to conduct a randomized, double blind, controlled trial that will evaluate effectiveness and tolerability of omega-3 fatty acids and inositol used alone and in combination. We plan to decrease the variability in the population under study by limiting the age range to 5-12 years and excluding cases with significant, untreated, comorbidity. We will measure cognitive effects/side effects with a neuropsychological battery pre and post treatment. We will exclude subjects with a history of failing treatment with two or more conventional treatments.

# **2. SPECIFIC AIMS**

Specific Aim I: Assessing the efficacy of omega-3 fatty acids versus inositol in the treatment of pediatric bipolar spectrum disorders. Our pilot work suggests that omega-3 fatty acids are effective in the treatment of bipolar disorder in youth, but no work has assessed the effectiveness of inositol for pediatric bipolar disorder. Hypothesis 1: Inositol will be as effective for pediatric bipolar disorder as omega-3 fatty acids.

Specific Aim II: Assessing the efficacy of omega-3 fatty acids plus inositol in the treatment of pediatric bipolar spectrum disorders. Omega-3 fatty acids exert a modest effect for pediatric bipolar disorder. Studies of inositol also report modest effects for depression. The combined treatment will be superior to either one used as monotherapy. Hypothesis 2: Omega-3 fatty acids plus inositol will be superior to either used alone in the treatment of pediatric bipolar spectrum disorders.

Specific Aim III: Assessing the side effect profile of omega-3 fatty acids plus inositol. Medications used to treat bipolar disorder in youth are fraught with side effects including sedation, extra-pyramidal symptoms, cognitive clouding, weight gain and diabetes. In contrast, omega-3 fatty acids and inositol have health benefits. Hypothesis 3: The combined use of omega-3 fatty acids plus inositol will have few side effects.

# **3. LENGTH OF STUDY**

The study will last up to 15 weeks from the initial phone screen (it could take up to three weeks to schedule and complete the initial screening process). Once subjects have completed the screening process, they will begin the 12-week treatment phase. Subjects will be assessed weekly throughout the study for effects and adverse effects.

# **4. SOURCE OF SUJECTS**

Individuals who respond to advertising will be screened for eligibility first by the study coordinator or a research assistant via phone and then by a study clinician. We will also be using Internet advertisements, including advertisements posted on Facebook, to recruit participants. Participants may also be recruited from the referral pool of existing

and new patients in the Pediatric Psychopharmacology Program, or via advertising in the local media. If a potential subject's clinician ascertains that the patient has an interest in study participation, the clinician will only offer contact information for the study to their patients. The patient can then contact the study coordinator for more information on the actual study. All subjects that enter the study will undergo standard screening and diagnostic procedures. Clinical records are not scanned in order to recruit subjects.

Subjects may also be recruited from one of our screening protocols: "Screening Protocol for Children and Adolescents with Bipolar and Bipolar Spectrum Disorder" (Protocol # 2001-P-001247) or "A General Screening Protocol for Child and Adolescent Research Studies in the Pediatric Psychopharmacology Program" (Protocol # 2014-P-001103). After participating in a screening protocol, subjects are assigned to specific studies based upon eligibility requirements (i.e. age, prior medication efficacy or tolerability).

Subjects who have completed a previous medication trial in our program may be eligible to participate in this study, as described in the Study Design section. Other medical records on a subject will not be used at any point.

# **5. SUBJECT ENROLLMENT**

All subjects that enter the study will undergo standard screening and diagnostic procedures. Written informed consent will be obtained from subjects' parent/guardian prior to initiation of the study protocol. Subjects aged 7 and older will sign age appropriate assent forms. The study subjects and their parent may take as much time as they feel necessary to consider their participation in the study as well as consult with their family members or physician. Only patients who are not responding to their current treatment regimen will be tapered from their medications to enter this study. Participation in this study is voluntary, and subjects may withdraw from the study at any time.

# 6. SUBJECT SELECTION CRITERIA

# A. Inclusion Criteria:

- 1. Male or female subjects, 5-12 years of age.
- Subjects must have a DSM-IV diagnosis of a bipolar spectrum disorder (type I, II, or Not Otherwise Specified (NOS)), and currently displaying mixed, manic, or hypomanic symptoms (without psychotic features) according to the DSM-IV based on clinical assessment and confirmed with structured diagnostic interview (Schedule of Affective Disorders and Schizophrenia for School-Age Children Epidemiological Version (K-SADS-E)) (Orvaschel, 1994).
- 3. Subjects and their legal representative must have a level of understanding sufficient to communicate intelligently with the investigator and study coordinator, and to cooperate with all tests and examinations required by the protocol.
- 4. Subjects and their legal representative must be considered reliable.
- 5. Each subject and his/her authorized legal representative must understand the

nature of the study. The subject's authorized legal representative must sign an informed consent document and the subject must sign an informed assent document.

- 6. Subjects must have an initial score on the YMRS total score of at least 20.
- 7. Subject must be able to swallow pills.
- 8. Subjects with ADHD and ODD will be allowed to participate in the study provided that the impairment associated with these disorders is of mild or moderate severity (not severe) and milder in severity relative to the impairment of the bipolar disorder, according to clinician evaluation. Subjects with comorbid anxiety disorders will be allowed to participate provided that the impairment associated with the anxiety is of minimal severity, according to clinician evaluation. Subjects with comorbid cD will be excluded.

# **B.** Exclusion Criteria:

- 1. Investigator and his/her immediate family; defined as the investigator's spouse, parent, child, grandparent, or grandchild.
- 2. Serious or unstable illness including hepatic, renal, gastroenterological, respiratory, cardiovascular (including ischemic heart disease), endocrinologic, neurologic, immunologic, or hematologic disease.
- 3. History of bleeding diathesis, including those with von Willebrand disease.
- 4. Uncorrected hypothyroidism or hyperthyroidism.
- 5. History of sensitivity to omega-3 fatty acids or inositol. A non-responder or history of intolerance to omega-3 fatty acid or inositol, after 2 months of treatment at adequate doses as determined by the clinician.
- 6. Severe allergies or multiple adverse drug reactions.
- 7. Failed 2 or more previous trials with anti-manic treatments including lithium, anticonvulsants and atypical antipsychotic medication.
- 8. Current or past history of seizures.
- 9. DSM-IV substance use, abuse or dependence (unlikely in ages 5-12).
- 10. Judged clinically to be at serious suicidal risk.
- 11. Current diagnosis of schizophrenia.
- 12. Current diagnosis of conduct disorder
- 13. Pregnancy (unlikely in ages 5-12).
- 14. YMRS Item #8 (Content) score of 8 ("delusions; hallucinations").
- 15. YMRS total score above 40.
- 16. Girls who have begun menstruating.
- 17. C-SSRS score  $\geq$  4.
- 18. IQ < 70.

We will enroll 90 subjects to allow for randomization of 30 subjects into each treatment arm of the study. The subject's first visit to the office consists of a meeting with a study clinician who explains the study, obtains informed consent, and administers an abbreviated form of the structured diagnostic assessment (45-90 minutes). After the evaluation with the study clinician, the subjects will undergo a neuropsychological assessment (45-60 minutes).

We anticipate that subjects may enter this trial following completion of/withdrawal from other Bipolar Disorder protocols in our office, and that there may be procedural overlap. So as to not burden subjects/parents/guardians with redundant time commitments, we will use the following data if previously collected:

- **Diagnostic Data:** If a subject has completed an evaluation with one of the study clinicians and/or the structured assessment within the previous 12 months prior to entrance into this study, they will not be asked to repeat any overlapping diagnostic procedures. However, the study clinician will review the interval time period to assess for clinically significant medical or psychiatric history, to ensure that the subject meets appropriate study entrance criteria.
- **Cognitive and Neuropsychological Testing:** If the subset of scales assessing intelligence (WASI or KBIT-2 for 5 year-olds) and cognitive functioning (select WISC tasks or WPPSI-III tasks for 5 year-olds) in the neuropsychological battery

have been completed within 12 months prior to entrance into this study, subjects will not be asked to repeat these procedures at screening/baseline.

• Screening Rating Scales: If a parent has completed the Child Behavior Checklist (CBCL), Social Responsiveness Scale (SRS), or the Behavior Rating Inventory of Executive Function – Parent Form (BRIEF) within the past six months as part of one of our screening protocols, we will not ask the parent/guardian to repeat these scales at screening/baseline.

Eligible subjects will be required to come into the office for weekly visits for the 12week study. During this time subjects will receive treatment with inositol, omega-3 fatty acids, or both. Subjects will be randomized to treatment arms in a double-blind fashion. Although every effort will be made to encourage subjects to keep regularly scheduled appointments, in the event that a subject is unable to come into the office within a reasonable timeframe of a scheduled study visit, and the treating research clinician feels that subject safety will not be jeopardized by doing so, the clinician may conduct the visit with the subject over the phone. During the phone visit, the clinician will complete all study scales for that visit. This will ensure that each subject will be continuously monitored by the clinician throughout the course of the study despite unforeseen scheduling circumstances. However, neither the study evaluation visit, nor the baseline visit, nor the final study visit may be conducted over the phone. Additionally, phone visits may not occur for two consecutive visits.

Vital signs (blood pressure, pulse, weight, height, temperature) will be measured at every visit. Those subjects who terminate study participation before the completion of the study will be asked to complete all tasks scheduled to take place on the final study visit at the time of study discontinuation.

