# 8. Neuropsychological Tests/Cognitive Evaluation

IQ Testing: At study beginning, subjects will complete a brief cognitive screen. The scales we will use meet the demand for quick reliable measures of intelligence in clinical, educational and research settings. These tests will provide estimates of verbal and nonverbal ability respectively, as well as the direct measure of Full Scale IQ. This portion of the cognitive evaluation will take

approximately 30 minutes to complete. In the unlikely event that a subject's estimated IQ is below 70, the subject will not be eligible to participate in the study. Depending upon the subject's age, the cognitive screen will consist of:

- **Subjects age 5:** Verbal Knowledge, Riddles, and Matrices subtests of the Kaufman Brief Intelligence Test, Second Edition (KBIT-2)(Kaufman & Kaufman, 2004)
- Subjects ages 6-12: Vocabulary and Matrices subtests of the Wechsler Abbreviated Scale of Intelligence (WASI)(Wechsler, 2003)
- Cognitive Functioning Testing: At screening and endpoint, to assess the impact of treatment on cognition, we will assess basic intellectual and cognitive functions purported to be deficient in patients with bipolar disorder. Cognitive deficits that have been observed in bipolar disorder may reflect dysfunction in the frontal subcortical circuits that support aspects of attention, executive functions processing speed, memory and learning (Bearden, 2001). The neuropsychological battery we have developed to assess these functions includes both published clinical measures with large, normative samples and experimental measures with strong empirical evidence of validity. This neuropsychological battery, which has been used widely in clinical trials and family studies in our office, has been well tolerated. The testing will take approximately 25 minutes to complete. The ageappropriate testing will include:
  - Subjects age 5: Symbol Search and Coding subtests of the Wechsler Preschool and Primary Scale of Intelligence (WPPSI-III) (Wechsler & Sattler, 2002) to measure processing speed
  - Subjects ages 6-12: Digit Span and Coding subtests from the Wechsler Intelligence Scale for Children-Fourth Edition (WISC-IV) (Wechsler, 2003) to measure working memory and processing speed

The working memory scale will be omitted for subjects who are 5 years of age, as we do not have an age-appropriate scale available.

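### Cognitive scores up to 12 months old, and SRS or BRIEF forms up to six months old, may serve as the pre-treatment value, so within-arm change need not reflect the 12 treatment weeks

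*Combined protocol and SAP*

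**What the plan says.** The Rationale in section 1 states the purpose: "We will measure cognitive effects/side effects with a neuropsychological battery pre and post treatment". Section 8, item 8 (Neuropsychological Tests/Cognitive Evaluation) schedules the cognitive tasks "At screening and endpoint, to assess the impact of treatment on cognition". The secondary-measures text in section 8 also makes the SRS and BRIEF parent forms pre-post measures.

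Section 7 then waives the pre-treatment assessment for some children. It expects that "subjects may enter this trial following completion of/withdrawal from other Bipolar Disorder protocols in our office". If the IQ scales (WASI or KBIT-2) and the selected WISC or WPPSI-III tasks "have been completed within 12 months prior to entrance into this study, subjects will not be asked to repeat these procedures at screening/baseline". CBCL, SRS and BRIEF are waived if completed "within the past six months as part of one of our screening protocols".

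Only the diagnostic-data bullet carries a safeguard: "the study clinician will review the interval time period to assess for clinically significant medical or psychiatric history". None is stated for the cognitive tasks, SRS or BRIEF.

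The cognitive instrument depends on age. At age 5 it is the "Symbol Search and Coding subtests of the Wechsler Preschool and Primary Scale of Intelligence (WPPSI-III"), with no working-memory measure. At ages 6-12 it is the "Digit Span and Coding subtests from the Wechsler Intelligence Scale for Children-Fourth Edition (WISC-IV").

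**The concern.** Reusing an IQ score or a CBCL is reasonable, because both are collected only at the start, to check entry or describe the groups. The WISC-IV/WPPSI-III subtests, SRS and BRIEF are different: the reused value becomes the baseline of an outcome.

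A reused score can predate another trial in the same programme. It can also predate the two weeks of stable medication required before entry, or the washout required before the Baseline Visit. The protocol itself names cognitive impairment and clouding among the side effects of existing drugs (sections 1 and 2). A child tested on such a drug and later taken off it could appear to improve for reasons unrelated to omega-3 or inositol.

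This matters because all three arms are active. A cognitive benefit or harm shared by all arms can be seen only in within-arm pre-post change, and that is the quantity an old baseline distorts. Nothing in section 9 excludes reused scores or adjusts for the length of the interval.

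**Working it through.** **The plan's own figures.** Section 9.C gives between-group power of 0.93 (alpha 0.05) and 0.81 (alpha 0.01) for 5 points with SD 10 on YMRS or CDRS, using one baseline and 12 follow-ups. The correlation is described only as high. A change-score variance factor of (1 + 11ρ)/12 + 1 − 2ρ with ρ = 0.71 is 0.734 + 1 − 1.42 = 0.314. With 30 per arm this gives 0.933 and 0.810, so the figures are attainable but cannot be confirmed. No power figure is given for cognition, SRS or BRIEF, and nothing below rests on these.

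**Interval.** Inputs are reuse limits of 12 months (52 weeks) and six months (26 weeks) from section 7, and 12 weeks of treatment and up to 3 weeks of screening from section 3.
- Cognition: 52 + 12 = 64 weeks, or 67 with screening. Treatment share is 12/64 = 18.8% or 12/67 = 17.9%.
- SRS and BRIEF: 26 + 12 = 38 weeks, or 41. Treatment share is 12/38 = 31.6% or 12/41 = 29.3%.
- With fresh baselines: 12 to 15 weeks, so the share is 100% to 80%.

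These are the limits for one child at the maximum age of data, not averages.

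**Within-arm change (illustration).** Assume a pre-entry drift of 0.2 or 0.4 SD in half the children, ρ = 0.7 and n = 30. Mean change without any treatment effect is 0.1 or 0.2 SD. The SD of change is √(0.6 + 0.25 × 0.2²) = 0.781 or √(0.6 + 0.25 × 0.4²) = 0.8. A nominal 5% pre-post test would then reject in about 11% or 28% of trials.

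**Between-arm precision.** With one pre and one post score, the ANCOVA standard error is proportional to √(1 − ρ²). The correlations are assumptions; the documents give none.
- Every child reuses data, ρ from 0.8 to 0.7: √(0.51/0.36) = 1.19, equal to 1.4 times the children.
- Every child reuses data, ρ from 0.8 to 0.6: √(0.64/0.36) = 1.33, equal to 1.8 times the children.
- A quarter reuse data (assumption; fresh and reused baselines taken to have equal mean and variance): pooled ρ is 0.75 × 0.8 + 0.25 × 0.7 = 0.775, or 0.75 × 0.8 + 0.25 × 0.6 = 0.75. Ratios are √(0.3994/0.36) = 1.05 and √(0.4375/0.36) = 1.10.

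For a difference of 0.5 SD with 30 per arm, the all-reuse case takes two-sided 5% power from 0.90 (ρ = 0.8) to 0.77 (0.7) or 0.68 (0.6).

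**Instrument.** A child tested at 5 a full year before entry is at least 6 at entry. If age at endpoint decides, that child gets WISC-IV. Symbol Search then has no endpoint value, Digit Span has no baseline, and Coding comes from two different instruments. The same can happen without reuse: with ages uniform over 5-12 (assumption), 90/8 = 11.25 children are 5 at entry and 11.25 × 12/52 = 2.6 turn 6 during treatment.

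**The case against.** The strongest reply is that the harm falls mainly on an analysis the plan does not specify. In section 9.B the only planned within-arm test concerns mania. The cognition hypothesis is exploratory and compares the combination with each single treatment at endpoint, and the side-effect test uses cumulative reports, not test scores. This stands, and it limits the weight of the point. It does not remove it, because the Rationale and section 8 promise a pre-post reading of cognition.

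A reader might infer that old baselines bias the comparison of arms. They do not: the scores precede randomisation, so reuse is balanced in expectation. A comparison of endpoint scores alone would not be touched at all.

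A reader might also infer that the plan changes the test at the sixth birthday. The documents do not say so. The under-6 rule appears under Screening Visit, section 8 does not fix the visit at which age is taken, and the last-visit testing is described as a repeat, which could mean the same test. A subtest called Coding is in both batteries. Nor can the roughly 11 children aged 5 at entry be counted as switching because of old baselines. With a year-old score they were tested at 4; the children at risk are mostly 6 at entry, and only those who reuse data.

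Finally, the waiver is a deliberate choice to spare families repeated testing. That is a fair aim, but it does not require reusing the baseline of an outcome.

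**Conclusion.** The point holds for within-arm change in the cognitive tasks, SRS and BRIEF among children who reuse data. At the permitted limits, treatment fills 18-19% of the measured interval for cognition and 29-32% for SRS and BRIEF. How far results would be distorted cannot be stated, because the number of such children is not given.

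For the exploratory between-arm contrast the cost is precision only: from about 5-10% on the standard error if a quarter reuse data to 19-33% if all do, under assumed correlations. The larger figures should not be read as the expected loss. YMRS and CDRS are not on the reuse list and are rated at the Baseline Visit, so the primary outcomes are unaffected.

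The endpoint instrument after a sixth birthday is an unspecified point. If WISC-IV is used, a child whose baseline was taken at 5 has no working-memory baseline and no same-instrument pair.

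**What to change.** In section 7, under previously collected data:
- Keep the 12-month waiver for IQ (WASI/KBIT-2) only, and the existing six-month waiver for the CBCL only.
- Give the WISC-IV or WPPSI-III subtests, SRS and BRIEF within this study's screening/baseline window for every child.

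In section 8, item 8, state that the endpoint uses the same cognitive instrument the child had at baseline. Reconcile the BRIEF schedule as well: its own entry lists baseline, middle and endpoint, the secondary-measures paragraph lists baseline and endpoint, and Table 1 as read here marks baseline only.

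The cost is about 25 minutes of testing and two parent forms for each child with prior data, and some added practice effect. The change does not require testing after washout. A child tapered during screening could still be tested before the taper; moving that testing would affect more children and is a separate decision.

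If the waiver must stay, the minimum is to record test date and instrument and to add a sensitivity analysis without reused baselines.
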